1791 analyses on an intention to treat basis (ITT). For patients who do not wish for their previously collected data
1792 to be used, we will exclude all data collected after the point of consent (i.e. ward movements, EQ-5D and
1793 follow-up data) from any analyses.

1794 Data on all withdrawals is captured on a specific case report form (CRF), and will be tabulated by allocation
1795 of the enrolling paramedic (**Table T3**).

1796 **3.7 Analysis populations**

- 1797 • **Population 1a:** The analysis population for the primary outcome (mRS at discharge/30-days) is all
1798 patients who receive resuscitation, are attended by an A2 paramedic and meet the eligibility criteria,
1799 i.e. all trial patients. This is also the analysis population for outcome 5 (chest compression fraction),
1800 but limited to two trusts and starting partway through the trial.

- 1801
- 1802
- 1803
- **Population 1b:** The analysis population for the second component of secondary outcome 6 (ROSC on ED arrival) is all patients who receive resuscitation, are attended by an A2 paramedic, meet the eligibility criteria and were conveyed to ED.
- 1804
- 1805
- 1806
- 1807
- **Population 2:** The analysis population for secondary outcomes 1 to 4, 6 and 7 (airway management details, but only covering ROSC during advanced airway management by A2 paramedic for outcome 6) is all trial patients who received at least one advanced airway management attempt by the enrolling A2 paramedic.
- 1808
- 1809
- **Population 3:** The analysis population for secondary outcome 8 (length of initial ICU stay) is all trial patients who were admitted to ICU.
- 1810
- 1811
- 1812
- **Population 4:** The analysis population for secondary outcome 9 (length of hospital stay) is all trial patients admitted to hospital who did not refuse consent (i.e. patients who either consent to active or passive follow-up or who die prior to approach).
- 1813
- 1814
- 1815
- 1816
- 1817
- **Population 5:** The analysis population for secondary outcomes 10 and 13 (EQ-5D health scores and state scores) and secondary outcomes 11 and 12 (time to death after discharge and mRS during follow-up) is all trial patients who consent to active follow-up, survive to 30 days/hospital discharge and provide relevant data for at least one of the three time points (30 days/hospital discharge, 3 months and/or 6 months).
- 1818
- 1819
- 1820

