1860 higher scores denoting higher Quality of Life (QoL)).

1861 Trial patients who did not survive to 30 days/hospital discharge will be assigned EQ-5D visual analogue scale
1862 and summary index scores of zero.

1863

1864 **5.4 Other variables**

New variable	Rules
POPULATION 0 and 1:	
Age	If date of birth ≠ missing: Age= (OHCA date – Date of birth) /365.25 If date of birth = missing: Age= approximate age (see section 4) Else missing
999 call to first crew arrival time (mins)	(First crew arrival date-incident date)*24*60 + (First crew arrival time-incident time)
POPULATION 1:	
Trial patient	If was resuscitation attempted=Yes and was incident attended by AIRWAYS-2 paramedic=Yes and did patient meet eligibility criteria=Yes, then = Yes

New variable	Rules
Survival status to hospital discharge	
If was resuscitation attempted=No or was incident attended by AIRWAYS-2 paramedic=No or did patient meet eligibility criteria=No, then = No
 
Else missing
 
If admitted to ED (Form D)=No, then = Died on scene
 
If admitted to ED=Yes, and survived to ICU admission (Form G)=No, then = Died prior to ICU admission
 
If admitted to ED=Yes, and survived to ICU admission=Yes, and survived to ICU discharge (Form G)=No, then = Died prior to ICU discharge
 
If admitted to ED=Yes, and survived to ICU admission=Yes, and survived to ICU discharge (Form G)=Yes, and transferred=Yes and level of care in transferred hospital (form G2)=Level 3 and survived to ICU discharge (Form G2)= No, then = Died prior to ICU discharge
 
If admitted to ED=Yes, and survived to ICU admission=Yes, and survived to ICU discharge=Yes and ((transferred = No) or (transferred=Yes and level of care admitted to is level 2 or 1) or (transferred=Yes and level of care admitted to is level 3 and survived to ICU discharge=Yes)) and (mRS (Form H2/I2)=6 or (mRS (Form H2/I2) ≠6 & has patient died since ICU discharge (but prior to hospital discharge) (Form W2) = Yes) or survived to hospital discharge (form H3/I3)=No), then = Died prior to hospital discharge
 
If admitted to ED=Yes, and survived to ICU admission=Yes, and survived to ICU discharge=Yes and ((transferred = No) or (transferred=Yes and level of care admitted to is level 2 or 1) or (transferred=Yes and level of care admitted to is level 3 and survived to ICU discharge=Yes)) and (mRS≠6 or survived to hospital discharge=Yes, then = Survived to 30 days/hospital discharge)

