Airway management in place when first ROSC was achieved or the resuscitation was discontinued if no ROSC was achieved	
if ('any ROSC achieved during airway management'=Yes and airway management first time ROSC was achieved=intubation) OR ('any ROSC achieved during airway management'=No and final airway attempt=intubation and 'was airway management handed over'=No), then = intubation
 
if ('any ROSC achieved during airway management'=Yes and airway management first time ROSC was achieved= i-gel) OR ('any ROSC achieved during airway management'=No and final airway attempt= i-gel and 'was airway management handed over'=No), then = i-gel

New variable	Rules
	
if ('any ROSC achieved during airway management'=Yes and airway management first time ROSC was achieved= any SGA) OR ('any ROSC achieved during airway management'=No and final airway attempt= any SGA and 'was airway management handed over'=No), then = other SGA if ('any ROSC achieved during airway management'=Yes and airway management first time ROSC was achieved=OPA/NPA) OR ('any ROSC achieved during airway management'=No and final airway attempt= OPA/NPA and 'was airway management handed over'=No), then = other Else missing

POPULATION 3:	
Duration of initial ICU stay	
For patients who survive to ICU discharge in admitting hospital and (were not transferred or were transferred to another hospital but at a lower level of care) = (ICU discharge date - ICU admission date)*24*60 + (ICU discharge time - ICU admission time)
 
For patients who are transferred from ICU in the admitting hospital to ICU (level 3 care) in another hospital and survives to ICU discharge in the transferred hospital = ((ICU discharge date on Form G2 - ICU admission date on Form G)*24*60 + (ICU discharge time on Form G2- ICU admission time on form G))
 
For patients who die in ICU in the admitting hospital (i.e. censored for analysis) = (ICU death date - ICU admission date)*24*60 + (ICU death time - ICU admission time)
 
For patients who are transferred from ICU in the admitting hospital to ICU (level 3 care) in another hospital and die in ICU in the transferred hospital (i.e. censored for analysis) = ((ICU death date on form G2 - ICU admission date on form G)*24*60 + (ICU death time on form G2 - ICU admission time on form G))

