ICU duration event/censor variable	
If survived to ICU discharge =Yes and transferred= No on form G, then = 1 If survived to ICU discharge =Yes and transferred= Yes on form G and survived to ICU discharge =Yes on form G2, then = 1 If survived to ICU discharge=No on form G, then = 0 If survived to ICU discharge =Yes and transferred= Yes on form G and survived to ICU discharge =No on form G2, then = 0 Else missing

POPULATION 4:	
Duration of hospital stay	
If survival status = survived to 30 days/hospital discharge and consent=active or consent=passive, then = (Hospital discharge date (Form H/I3) - ED admission date (Form G)) *24*60 + (Hospital discharge time (Form H/I3) - ED admission time (Form G))

New variable	Rules
	
If survival status= died prior to ICU admission or survival status= died prior to ICU discharge or (survival status=died prior to hospital discharge & ((consent status=active or passive) or patient was not approached)), then = (Date of death - ED admission date (Form G)) *24*60 + (Time of death - ED admission time (Form G)) Else missing

Hospital duration event/censor variable	
If survival status =survived to 30 days/ hospital discharge and consent=active or consent=passive, then = 1 If survival status= died prior to ICU admission or survival status= died prior to ICU discharge or (survival status=died prior to hospital discharge & ((consent status=active or passive) or patient was not approached)), then = 0 Else missing

Timing of (patient) withdrawal	
if date of withdrawal from study < date of discharge, then = pre-discharge if date of withdrawal from study > date of discharge, then = post-discharge Else missing

Decision taken by	
if healthcare professional's decision=Yes and (patient choice = No or missing), then = health care professional if healthcare professional's decision=No or missing and patient choice = Yes, then = patient Else missing

1865

1866

1867 **6. STATISTICAL ANALYSES**

1868 **6.1 Baseline data**

1869 Baseline characteristics (i.e. patient demography and initial cardiac arrest details) will be described grouped
1870 by the allocation of the first A2 paramedic on scene for all trial patients (see **Table T4**). Intervention details
1871 will also be described for all trial patients (see **Table T5**).

1872 Continuous variables will be summarised using the mean and standard deviation (SD) (or median and inter

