1898 All outcomes listed in Sections 2.3 and 2.4 will be presented as per the template tables **Table T6** to **T8** and
1899 may also be presented graphically. General methods of presentation and assessing intervention effects are
1900 outlined below. For formal comparisons the intubation group will be the reference group. Details specific to
1901 each outcome are described as appropriate. Secondary outcomes 10 to 13 will not be reported in the primary
1902 outcome paper.

Date type	Outcomes
Binary	mRS (at discharge/30days) Initial ventilation success Regurgitation/aspiration Loss of previously established airway Return of spontaneous circulation (ROSC) 72h survival
Categorical	Actual sequence of airway interventions delivered ¹ Airway management in place when ROSC was achieved or resuscitation was discontinued or intervention from A2 paramedic stopped ¹
Continuous	Chest compression fraction

	Duration of ICU stay (presented separately for survivors and patients who die during ICU stay) ¹
	Duration of hospital stay (presented separately for survivors and patients who die during hospital stay) ¹
Time to event	Time from OHCA to when discharge/30 day mRS was assessed ^{1,3} Time to death ² Time to death (up to 72h)
Longitudinal	mRS (at discharge/30days, 3 months and 6 months) EQ-5D index score and visual analogue scale score (at discharge, 3 months and 6 months)

1903 *Note:-*

1904 ¹ These outcomes will be described but not formally compared

1905 ² Time to death will be formally compared in place of length of ICU and hospital stay

1906 ³ This is not a specified outcome but the DMSC raised it as a point of interest.

1907

1908 • **Binary outcomes** will be presented as numbers and percentages of patients in the category of interest.
1909 Outcomes will be compared between intervention groups using logistic regression. The intervention
1910 comparison estimate will be presented as an adjusted odds ratio (OR) with a 95% confidence interval
1911 (95% CI) and p-value. Formal statistical comparisons of treatment effects will only be performed if more
1912 than ten patients in total experience the outcome (with at least one event in each treatment group). .

1913 • **Categorical outcomes** will be presented as numbers and percentages of patients in each category.
1914 Outcomes will be compared between intervention groups using multinomial logistic regression.
1915 Treatment comparison estimates will be presented as adjusted odds ratios (OR) and 95% confidence

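### The ICU event/censor rule has no branch for survivors transferred to a lower level of care, contradicting the duration and survival-status rules beside it

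*Protocol*

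**What the plan says.** Three derivations in SAP section 5.4 classify the same ICU patient.

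- **Duration of initial ICU stay.** Survivors of the first ICU who "were not transferred or were transferred to another hospital but at a lower level of care" form one group. Their stay runs from ICU admission to ICU discharge in the admitting hospital.
- **Survival status to hospital discharge.** A patient meeting "transferred=Yes and level of care admitted to is level 2 or 1" is accepted as an ICU survivor with no further ICU question. The second ICU-discharge answer is asked for only in the other case: "transferred=Yes and level of care admitted to is level 3 and survived to ICU discharge=Yes".
- **ICU duration event/censor variable.** Code 1 is reached by two lines, "If survived to ICU discharge =Yes and transferred= No on form G, then = 1" and "If survived to ICU discharge =Yes and transferred= Yes on form G and survived to ICU discharge =Yes on form G2, then = 1". Code 0 is given for death in the first ICU, or under "If survived to ICU discharge =Yes and transferred= Yes on form G and survived to ICU discharge =No on form G2, then = 0". Everything else is missing.

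On use, SAP section 3.7 says of Population 3: "The analysis population for secondary outcome 8 (length of initial ICU stay) is all trial" patients admitted to ICU. The outcome table in SAP section 6.2.2 lists "Duration of ICU stay (presented separately for survivors and patients who die during ICU stay" among the continuous outcomes, and its notes say that the outcome is described but not formally compared. Skeleton Table T7 has one duration row for ICU survivors, one for ICU deaths and one for all patients admitted to ICU.

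**The concern.** The first two rules separate step-down transfers (level 1 or 2) from ICU-to-ICU transfers (level 3). The third does not. It treats every transfer as if a second ICU stay followed and waits for the outcome of that stay on Form G2. A patient stepped down to a ward or level 2 bed elsewhere has no second ICU stay to report.

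Length of ICU stay is a listed secondary outcome that must be shown separately for survivors and deaths, so some indicator has to make the split. The event/censor variable is the only such indicator defined under the Population 3 heading, and the duration rule marks ICU deaths as censored in step with it. An analyst could reasonably split on it. The rule would then remove survivors only, and a selected kind: those fit for a lower level of care in another hospital. The gap would also appear as missing data when it is in fact an effect of the coding.

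**Working it through.** The plan gives no figure to reproduce. The check applies the duration rule and the event/censor rule literally to each relevant combination of Form G survival, transfer, receiving level and the Form G2 ICU-discharge item.

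| Form G: left ICU alive | Transferred | Receiving level | Form G2 item | Duration rule | Event code |
|---|---|---|---|---|---|
| Yes | No | – | – | Form G stay, survivor | 1 |
| Yes | Yes | 1 | blank | Form G stay, survivor | **missing** |
| Yes | Yes | 2 | blank | Form G stay, survivor | **missing** |
| Yes | Yes | 2 | Yes | Form G stay, survivor | 1 |
| Yes | Yes | 2 | No | Form G stay, survivor | **0** |
| Yes | Yes | 3 | Yes | Form G admission to Form G2 discharge, survivor | 1 |
| Yes | Yes | 3 | No | Form G admission to Form G2 death, censored | 0 |
| No | No | – | – | Form G admission to death, censored | 0 |

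1. The two rules agree for untransferred patients, for level 3 transfers with a Form G2 answer, and for deaths in the first ICU.
2. They disagree only for level 1 or 2 transfers. With a blank Form G2 item, the patient has a completed survivor duration and no event code. With 'No', the patient has a survivor duration and the code used for an ICU death. Only a recorded 'Yes' gives the right code.
3. The survival-status rule sides with the duration rule: all three bold rows are ICU survivors under it.
4. Effect on the survivor row, if it is selected by event code 1: let S be the number of ICU survivors and f the share of them transferred at level 1 or 2 without a 'Yes' on Form G2. The row then holds S × (1 − f) patients, so the share lost is f.
5. Size: the documents support only the denominator. With 9,070 patients (Protocol section 4.7), 20% reaching hospital admission (section 4.6.2) and about half of those going to ICU (section 4.5.3), 9,070 × 0.20 × 0.5 = 907 ICU admissions. Neither S nor f is given.

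**The case against.** The strongest reply is that the variable may do no work. No section names it as the splitting variable. The split could be made from the Form G survival item or from survival status, which handles these patients correctly. No time-to-event analysis of ICU stay is planned, because time to death is formally compared in its place. The same rule applies to both arms, and no mechanism for a between-group bias has been shown. SAP section 6.2.7 has missing data footnoted in all tables, so missing codes would be visible. Form G2 is not shown, and a recorded 'Yes' would give the right code.

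All of this limits the consequence, and it stands. It does not remove the contradiction. A blank item is what the survival-status rule implies, since it consults the item only after a level 3 transfer, and a 'No' would be worse than a blank. A footnote would report the gap without showing that a coding rule caused it.

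Four stronger readings are tempting and are not supported:

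- A reader might infer that ICU stay will be summarised without these patients. They have a duration, they belong to Population 3, and exclusion depends on a choice of splitting variable that the SAP leaves open.
- A reader might infer that the all-patients summary is weighted towards deaths. That row of Table T7 needs a duration and no event code.
- A reader might take the remark on transfers in Protocol section 5.6.3 as evidence that step-downs are common. It describes survivors moving towards heart attack centres and major receiving hospitals, and says nothing on how often patients go to lower-level care.
- A reader might attach a count. Assuming 40–60% ICU survival and 10–30% step-down transfer gives 907 × 0.4 × 0.1 ≈ 36 to 907 × 0.6 × 0.3 ≈ 163. Neither rate comes from the documents. The survival rate also sits badly with the plan's 9% surviving to discharge (9,070 × 0.09 ≈ 816), because the survival-status rule routes those survivors through ICU.

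**Conclusion.** The inconsistency is real and lies in the current text: one of three companion rules omits a branch that the other two contain. Survivors moved to level 1 or 2 care get a missing event code if the Form G2 item is blank, as the survival-status rule implies but no section states, and an ICU-death code if it is 'No'. The harm is conditional. It arises only if this variable splits the ICU-stay rows, and it is then confined to those split rows: a blank item removes the patient from the survivor row, and a 'No' moves the patient to the death row. The number of patients is unknown. The point is minor, because it concerns a secondary outcome that is described and not tested.

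**What to change.** In the ICU duration event/censor variable (SAP section 5.4):

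1. Add a line giving code 1 to a patient who left ICU alive and was transferred according to Form G, where Form G2 shows receiving level 1 or 2, whatever the Form G2 ICU-discharge item holds.
2. Restrict the two existing lines that use that item to receiving level 3.
3. State in SAP section 6.2.2, or in a note to Table T7, that this variable defines the survivor and death rows for ICU stay.

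The cost is one new line, two added conditions and one sentence, with the matching code, recorded as an SAP amendment and re-approved as SAP section 1.2 requires. No new data are needed: the survival-status rule already reads the level of care from Form G2.
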